There are several studies evaluating various supplementation regimens in preterm infants; however, considerable attention has not been given to the role of maternal vitamin D supplementation and its effects on preterm neonate's vitamin D status. Many groups have recommendations on vitamin D supplementation that have failed to form a consensus or have differing recommendations for preterm neonates. The AAP Committee on nutrition recommends 200-400 IU of vitamin D for very low birthweight infants (VLBW). On the other hand, the European Society of Pediatric Gastroenterology and Nutrition (ESPGAN) recommends 800-1600 IU daily (13). Due to the lack of substantial data, these various groups fail to make recommendations on arguably those at highest risk--preterm, very low birthweight (VLBW) infants, and extremely low birthweight (ELBW) infants. Along with variations in supplementation recommendations, there are also variations among scientific groups as to an ideal target 25(OH)D level. The AAP recommends 25(OH)D > 20 ng/mL (50 nmol/L) (14) and in the same year another group published a paper with recommended 25(OH)D > 30 ng/mL (75 nmol/L) (15). The Endocrine Society targets >30 ng/mL (75 nmol/L) (16) while ESPGAN >32 ng/mL (80 nmol/L) (13). Previous groups have looked at the effects of various vitamin D supplementation regimens in preterm infants, many of which have not shown significant changes in infant 25(OH)D concentrations, but have shown that higher supplementation leads to improved length, head circumference, and possibly immune function (17). Previous studies have shown safety of increased vitamin D supplementation with 800 IU and 1000 IU without significant toxicity (18-20).

In a previous randomized control trial performed at this institution by [name] and colleagues, maternal supplementation with 6400 IU/day of vitamin D₃ was more effective in achieving

vitamin D sufficiency in mothers without increased risk to infants or mothers (21, 22). This present pilot study plans to replicate this in mothers and their preterm infants (22). See IRB application attachments for this paper that is *in press*.

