5.0 Inclusion and Exclusion Criteria/ Study Population

Only women 18-45 years who are lactating and their preterm infants (<35 weeks) within the first week postpartum will be eligible for the study. Men will be excluded on the basis of the study criterion of lactation. Infants of both genders will be followed along with their mothers. Women who deliver at MUSC will be eligible for participation.

- a. **Inclusion Criteria for Lactating Women:** Women with documentation of fully breastfeeding who present within one month of delivery, who are 18-45 years old and in good general health will be eligible for participation.
- b. **Exclusion Criteria for Lactating Women:** Women with preexisting type I or type II diabetes, hypertension requiring medication or parathyroid disease will not be eligible for participation in the study. Those women with active thyroid disease will not be eligible for inclusion in the study; however, women who have normal thyroid parameters on thyroid replacement hormone will be eligible for participation in the study. In addition, because of

the potentially confounding effect of multiple gestations/births (e.g. twins, triplets), women with multiple gestations/births will not be eligible for participation in the study.

No racial or ethnic groups will be excluded from this study.

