3. Daily Vitamin D Supplementation: Infants of mothers who receive 600 IU of vitamin D₃ will receive 400 IU of vitamin D₃ in the form of drops. Infants of mothers who receive 6600 IU of vitamin D₃ will receive placebo drops.

3. General Health Assessment of Infant: At 1 week after delivery and then monthly until 3-months of age, each enrolled infant will undergo a growth (measuring head circumference, weight, length, head circumference, Ponderal index, body mass index [BMI]) and general health assessment.

4. PEAPOD Assessment: Prior to discharge from the NICU, the infant will also be placed in the PEAPOD® for body mass composition analysis. The material and data will be specifically obtained for research purposes. There is minimal risk. This is a safe device in which the infant lays in for 2 minutes.

5. Blood Sample from Infant: At initial visit, 1-, 2- and 3-months of age, each infant will have a blood sample 4mL (<1tsp) taken from either a vein (infant’s hand, arm or foot) or the heel. Total amount obtained will be less than 12mL (<1 1/2 tablespoon). The serum sample will be analyzed for vitamin D and calcium concentration. Parents will be counseled that if their infant is vitamin D deficient, the infant’s primary care physician and they will be contacted regarding the finding(s) with recommended follow-up.

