- b. **Infant:** The total amount of blood to be drawn during the study period (initial visit and months 1, 2, and 3) will be 2 mL at each visit (less than a teaspoon or less than 0.6% of the infant's total blood volume) or 10 mL (<2 tablespoons) over the course of 3 months. Using aseptic technique, blood will be drawn from the infant's hand, arm or heel either via venipuncture or heel stick. As with any blood draw, there may be a slight pain when the needle is inserted into a vein. Momentary discomfort may occur when skilled technicians or nurses perform phlebotomy. Pressure will be applied to the arm following the procedure to minimize the risk of bruising; however, despite these efforts, a bruise may form at the site. Lastly, there is a slight chance of inflammation of the vein and/or blood clot formation, but this is extremely rare.

2. The Risks of Randomization in the Study:

- a. There is a possibility that the treatment that each subject receives may prove to be less effective or to have more side effects than the other study treatment(s) or other available treatments. Because the ideal dose of vitamin D during lactation for mothers of preterm infants is unknown presently, the only way to determine the optimal dose is through a well-controlled, well designed scientific study that we are attempting to initiate.

3. The Risks of High Dose Maternal Vitamin D Supplementation are hypercalciuria and hypercalcemia.

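### The risk section's figure of under 0.6% of blood volume for a 2 mL infant draw is too low at the first draw for essentially every infant eligible under Section 5

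*Protocol*

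**What the plan says.** Section 15, item 1b (infant phlebotomy) gives the draw as "2 mL at each visit (less than a teaspoon or less than 0.6" per cent of the infant's total blood volume. The sentence applies this to the "initial visit and months 1, 2, and 3", that is, four draws, and does not limit it by weight or age. It gives the cumulative volume as "or 10 mL (<2 tablespoons) over the course of 3 months".

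Section 10 (Infant, item 5) gives a different volume: "each infant will have a blood sample 4mL (<1tsp) taken from either a vein", and "Total amount obtained will be less than 12mL".

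Section 5 makes eligible lactating women and "their preterm infants (<35 weeks) within the first week postpartum". No lower limit on birth weight or gestational age appears there or elsewhere. Section 10 (Infant, item 1) places the first visit at about 3 to 7 days of life. The background (Section 2) singles out "preterm, very low birthweight (VLBW) infants, and extremely low birthweight (ELBW) infants" as arguably at highest risk, and no criterion excludes them.

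**The concern.** A share of blood volume depends on the size of the infant. One unqualified ceiling for all visits can hold only if every infant is large enough at every visit. Back-calculation gives an infant about the size of a term newborn or older, whereas the trial first draws blood from preterm infants in the first week of life.

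This is the only place where the risk section sets the infant sampling burden against the infant's blood volume. The error runs in the reassuring direction and is largest for the smallest infants, who are eligible without restriction. No endpoint, analysis, sample size or safety limit depends on it. What is at stake is whether the stated risk is accurate.

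**Working it through.** **Inputs from the protocol**
- Draw of 2 mL, stated as under 0.6% of blood volume; four draws; total 10 mL (Section 15, item 1b).
- Draw of 4 mL; total under 12 mL (Section 10, Infant, item 5).
- Infants under 35 weeks, no weight or gestation floor (Section 5); first visit at about 3 to 7 days (Section 10, Infant, item 1).

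**Assumptions, not in the protocol**
- Blood volume of 80 to 100 mL/kg.
- Illustrative weights of 1.0 to 2.5 kg at the first draw, plus 4.0 kg to show where the statement becomes true.

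**Step 1. What the stated figure implies.** Blood volume needed = draw / 0.006.
- 2 mL: 2 / 0.006 = 333 mL. Weight: 333/100 = 3.3 kg to 333/80 = 4.2 kg.
- 4 mL: 4 / 0.006 = 667 mL. Weight: 667/100 = 6.7 kg to 667/80 = 8.3 kg.

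**Step 2. Can another mL/kg value rescue it?** Value needed = 333 / weight.
- 2.5 kg: 133 mL/kg.
- 1.5 kg: 222 mL/kg.
- 1.0 kg: 333 mL/kg.

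All lie well above the assumed range. Even at 120 mL/kg the infant would have to exceed 333/120 = 2.8 kg. The direction of the error at entry does not turn on the exact mL/kg chosen.

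**Step 3. Share of blood volume by weight.** Share = draw / (weight × mL/kg). Each range runs from 100 down to 80 mL/kg.

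| Assumed weight | 2 mL draw | Multiple of 0.6% | 4 mL draw |
|---|---|---|---|
| 1.0 kg | 2.0%–2.5% | 3.3–4.2 | 4.0%–5.0% |
| 1.5 kg | 1.3%–1.7% | 2.2–2.8 | 2.7%–3.3% |
| 2.0 kg | 1.0%–1.25% | 1.7–2.1 | 2.0%–2.5% |
| 2.5 kg | 0.8%–1.0% | 1.3–1.7 | 1.6%–2.0% |
| 4.0 kg | 0.5%–0.6% | 0.8–1.0 | 1.0%–1.25% |

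**Step 4. Totals over four draws.**
- Section 15: 4 × 2 = 8 mL, against 10 mL stated.
- Section 10: 4 × 4 = 16 mL, against under 12 mL stated.

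Neither total matches its own per-draw volume, and the two sections disagree on both figures. The percentage cannot be corrected until the volume is settled. Settling the volume does not correct it either: at 2 mL it stays too low at entry, and at 4 mL it is further off.

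**The case against.** The objections bear on the size and reach of the error.

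- **Several-fold understatement across the trial.** A reader might infer this, but the protocol does not support it. On the 2 mL to which the 0.6% is attached, the multiple is 1.3 to 1.7 at 2.5 kg and 1.7 to 2.1 at 2.0 kg. Larger multiples need the smaller infants or the 4 mL of Section 10.
- **A figure that fits no enrolled infant.** This too goes further than the text allows. The statement covers visits to month 3, and some infants may have reached 3.3 to 4.2 kg by then. The claim is firm for the first draw only.
- **Inputs from outside the protocol.** Neither mL/kg nor expected weights are given, so the multiples are illustrative. Step 2 shows that the direction does not depend on the exact mL/kg.
- **VLBW and ELBW infants.** The background mentions them when discussing gaps in recommendations, not as a forecast of enrolment. The point rests on the missing floor in Section 5, not on that passage.
- **Consent form.** It is tempting to say that parents are given the 0.6% figure. The consent pages are not available, so this cannot be checked.
- **Overlap with the volume conflict.** The 2 mL against 4 mL disagreement is firmer because it lies wholly within the protocol, and the two are best corrected together. The percentage is still a separate error, as Step 4 shows.

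All of these limits stand. None makes the percentage true at the first draw.

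**Conclusion.** The concern holds in a limited form. As written, the under-0.6% statement needs more than 333 mL of blood, about 3.3 to 4.2 kg at an assumed 80 to 100 mL/kg. It is too low at the first draw for essentially every eligible infant, on the assumption that infants born before 35 weeks weigh less than this at 3 to 7 days. It may become true for larger infants at later visits.

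Over assumed weights of 1.0 to 2.5 kg, 2 mL is about 0.8% to 2.5% of blood volume, roughly 1.3 to 4 times the stated ceiling. At 4 mL it is about 1.6% to 5%. The direction is secure; the multiples depend on weights and a mL/kg value that the protocol does not give. The statement should be corrected because it understates a burden on a vulnerable population. The design and analysis are unaffected.

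**What to change.** 1. Reconcile Section 10 (Infant, item 5) with Section 15 (item 1b): per-draw volume (4 mL against 2 mL) and total (under 12 mL against 10 mL), so that the total equals the per-draw volume times the four draws.
2. Check the reconciled volume against the population that Section 5 admits.
3. Replace the single ceiling in Section 15 with a percentage range over the expected weights at entry and at later visits, stating the mL/kg assumption.
4. If other participant-facing text carries the same percentage, bring it into line.

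The protocol's figures do not show which volume is intended, and this review does not propose one. Whether any sampling limit is needed, and what it should be, is for the sponsor and ethics board.

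The cost is a wording amendment and a less favourable stated burden at entry.

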1.0 Objectives / Specific Aims

The overall goal of this study is to assess maternal vitamin D status along with diet, and milk composition to, in turn, evaluate if infant vitamin D status can be improved with increased maternal supplementation and diet education. Our **central hypothesis** is that by maximizing maternal vitamin D status, there will be an increase infant 25(OH)D concentration in breastfed, preterm infants. This hypothesis will be tested by performing the following Specific Aims.

Aim 1: Determine the efficacy, effectiveness, and safety of maternal and premature infant vitamin D supplementation as a function of maternal vitamin D status, lactation status, and ethnicity.

H₁: Maternal supplementation of high dose (6,600 IU) vitamin D₃/day will be safe for lactating mothers.

H₂: It is anticipated that only high dose (6,600 IU) vitamin D₃/day supplementation of lactating mothers will provide sufficient antirachitic activity in breast milk to prevent vitamin D deficiency in nursing premature infants, regardless of ethnicity/race.

H₃: High-dose maternal supplementation will be safe and more effective than infant vitamin D supplementation alone, without any adverse side effects or health consequences in the mother or infant.

Consented lactating women who delivered preterm infants <35 weeks' gestation admitted to the MUSC NICU will be randomized 3-7 days following delivery to either 1 of 2 study groups: Group A (standard therapy of 600 IU vitamin D₃/day), Group B (high dose supplementation of 6,600 IU Vitamin D₃/day). As such, infants whose lactating mothers are randomized to the 600-IU/day group will receive 400-IU/day oral vitamin D₃ (recommended practice). Those infants of lactating mothers assigned to Group B will receive placebo. Calcium homeostasis will be monitored in all groups. Safety will be assessed throughout the study on a case-rather than a treatment arm basis using cautionary levels as the stop rule with intervention prior to exceeding normal urinary calcium/creatinine ratios in mothers and serum calcium concentrations in both mothers and infants. Through these proposed studies, the prevalence of vitamin D deficiency among mothers and their infants, and the utility of maternal therapeutic intervention with vitamin D₃ will be assessed.

Aim 2: Aim 2: Evaluate and maximize maternal milk composition.

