4.0 Study Endpoints

- Primary outcomes will be:
 - Infant total circulating 25(OH)D concentration at 3 months
 - Mother total circulating 25(OH)D concentration at 3 months
- Primary or secondary safety endpoints
 - Maternal serum calcium concentration initially and at months 1-, 2-, and 3
 - Maternal urine calcium/creatinine ratios initially and at months 1-, 2-, and 3
 - Infant serum calcium concentration at time points initially and at months 1-, 2-, and 3

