6. Laboratory Data from Blood and Urine Samples: At initiation of the study and at each monthly visit (1, 2, and 3), each woman will have blood sample drawn (20 mL) for detailed analysis of vitamin D and calcium homeostasis. The total blood to be drawn from woman during the 3-month study period will be 60mL (<1/2 cup). In addition, she will be asked to provide a urine sample to measure her urinary calcium/creatinine. A total of up to 4 blood and urine samples will be obtained from each mother, depending on continued participation in the study.

7. Milk Samples: At time of initiation of the study and at each monthly visit (1, 2, and 3), each mother will provide a milk sample from her left breast. The skin will be washed with warm water prior to pumping. The amount obtained will be less than 20 mL at each visit. This milk can be pumped that day and kept refrigerated or pumped at time of visit. This will then be run on the Calais Milk Analyzer to be tested for Fat, Total Protein, True Protein, Lactose, and Calorie/ounce.

8. Degree of Skin Pigmentation will be measured at each visit using the Smart Probe 400, a commercially available spectrometer, which is placed lightly on the skin. Sites to be measured include the inner and outer lower arm and the buttocks.

9. Depression/Anxiety Screening: Each mother enrolled in the study will complete the Edinburgh Postnatal Depression Scale (EPDS) at each monthly study visit. Women who score above the threshold consistent with possible depression will be referred to the appropriate trained professional. Any woman who responds “yes” to the suicide related statements in the EPDS will be immediately referred to the Emergency Room for further evaluation and treatment.

Infant

1. Outpatient Visits: Each mother will be asked to bring her infant as a scheduled outpatient at her monthly visits. If still admitted to the NICU, these monthly visits will be held in the MUSC NICU. If discharged, visits will be held at Infant High-Risk Clinic or NEXUS clinic. These visits will be the initial at approximately 3-7 days of life, then at months 1, 2, and 3.

2. Questionnaires: We will ask each mother to complete a questionnaire about her baby’s dietary type (breastfeeding, formula-supplementation), and feeding frequency for the week prior to each outpatient visit. Each questionnaire will take approximately 5 minutes to complete. See maternal section table.

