11.0 Specimen Collection and Banking

Blood, urine and milk specimens will be collected. The specimen will be marked with patient name, subject ID, date and time of collection as well as MRN. This is necessary to ensure integrity of the data is maintained. These specimens will be stored in a double

locked laboratory maintained by [name] and [name] in the Darby Children's Research Institute (DCRI), Room 304. The specimens will be stored for up to 5 years. The PI and the co-investigators as listed on the IRB application will have access to the specimens and associated data and will be responsible for receipt or transmission of them. Specimens will not be sent to an outside facility.

Specimen/Banking for Future Use

- Describe the linkages to subjects and who will have access to subject identities.
 - Specimens will be stored in -80°C freezer with study ID and participant name, MRN on samples. The samples will be located in the double locked lab of Drs. [name] and [name]. These samples will be destroyed after 5 years.
 - This information will be maintained in a database and all other data, including results of the study will be in a separate database that is password protected with the results by subject ID.
- List the data to be stored or associated with each specimen.
 - In one password-protected database: subject ID, participant name, MRN
 - In a separate password-protected database: subject ID, results
- State whether samples could be used for genetic analysis.
 - Yes, blood samples will be used for genetic polymorphisms of vitamin D binding proteins as this can affect vitamin D metabolism and processing and well as overall vitamin D status.
- Can specimens be withdrawn? If so, what is the process.
 - Yes, if a mother wants her samples withdrawn, she will inform the PI in writing of her request and sample(s) will be destroyed. This will be documented in the database and in the participant research record.

[figure not shown]

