hypercalciuria and hypercalcemia. There is a small risk that the woman's blood calcium level would increase in response to higher dose vitamin D supplementation. The body responds by excreting calcium in the urine to maintain normal calcium levels. If calcium levels in the blood continue to rise, then serum calcium will increase leading to hypercalcemia. This process takes weeks to months to occur. It takes approximately 3 months to reach steady state on an increased vitamin D intake/regimen. In related studies conducted at MUSC comparing maternal vitamin D supplementation with 400, 2400, or 6400 IU of vitamin D₃/day and their infants for 7 months, there were no differences in infant or maternal safety parameters (22). There were no reported episodes of either hypercalciuria or hypercalcemia in any of the treatment groups. In fact, maternal 25 (OH)D levels were higher in the 6400 IU/day treatment group compared to the 400 IU group. In breastfed infants, there was no statistical difference in the average circulating 25 (OH)D in either treatment arm (22).

- a. To ensure that each lactating mother and her breastfeeding infant and each nonlactating mother (and her formula-feeding infant as a control) maintain normal vitamin D status throughout the study period and not develop hypervitaminosis D, both mother and infant will be screened monthly for hypercalciuria, the first indicator of hypervitaminosis D. All study subjects will be monitored closely for hypervitaminosis D. Operationally, we define caution limits as urinary Ca/creatinine ratio > 0.8 mmol/mmol. Whenever any patient

exceeds the caution limit, a specific case study will be initiated by the Data Safety and Monitoring Committee (DSMC) to examine the contribution of sunlight exposure and other confounding factors. Operationally, we define upper limits as a urinary calcium/creatinine ratio > 1.0 mmol/mmol Ca/creatinine ratio. This is a conservative upper limit as circulating levels achieved in individuals living in sun-rich environments achieve this amount without causing toxicity. The DSMC will be convened to review any patient who exceeds any predefined toxic limit for any outcome. If the elevated levels are unexplained, the patient will be withdrawn from supplementation but will continue to be monitored.

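### The risk section promises monthly infant hypercalciuria screening against urinary limits, but the protocol schedules no infant urine; separately, a calcium threshold pairs incompatible units

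*Protocol*

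**What the plan says.** All references are to the protocol.

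- **Section 15 (Risks to Subjects), item 3a:** "both mother and infant will be screened monthly for hypercalciuria, the first indicator of hypervitaminosis D". The caution limit is a urinary calcium/creatinine ratio above 0.8 mmol/mmol and applies to any patient; exceeding it starts a DSMC case study. The upper limit is the same ratio above 1.0 mmol/mmol. The DSMC also reviews anyone who exceeds a toxic limit set in advance, whatever the outcome. The item includes nonlactating mothers and formula-fed control infants.
- **Section 1.0, Aim 1:** cautionary levels serve "as the stop rule with intervention prior to exceeding normal urinary calcium/creatinine ratios in mothers and serum calcium concentrations in both mothers and infants".
- **Section 4.0:** the safety endpoints include "Maternal urine calcium/creatinine ratios initially and at months 1-, 2-, and 3" and "Infant serum calcium concentration at time points initially and at months 1-, 2-, and 3". No infant urine endpoint is listed.
- **Section 5.0:** enrolment is limited to lactating women and their preterm infants: "Only women 18-45 years who are lactating and their preterm infants (<35 weeks" of gestation.
- **Section 10.0, Mother, item 6:** "she will be asked to provide a urine sample to measure her urinary calcium/creatinine".
- **Section 10.0, Infant, item 5:** the infant gives blood. "The serum sample will be analyzed for vitamin D and calcium concentration".
- **Section 11.0:** "Blood, urine and milk specimens will be collected", without saying from whom. Section 12.0 mentions urine samples of both mother and infant, but only in describing how they are labelled.
- **Section 14.0:** hypercalciuria leads to exit for the mother only; hypercalcemia does so for mother or baby.
- **Section 15, item 4:** one step for the infant depends on a serum calcium below 7.5 mg/dL, with 18.75 nmol/L given in brackets as the equivalent.

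**The concern.** Two of the three Aim 1 hypotheses, H1 and H3, concern safety, and H3 includes the infant. Item 3a presents hypercalciuria as the earliest sign of too much vitamin D and says infants are checked for it every month. Staff who follow the visit procedures would not collect the specimen that this check needs. A safeguard described in the risk section would then not be delivered to infants, and the only upper-side calcium limits printed as numbers could never be applied to them. The unit error is a different defect, but it sits inside a threshold that triggers action for an infant, so the two printed values cannot both be used.

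**Working it through.** **Infant urine.** No formula applies. The check compares every section that mentions urine, hypercalciuria or serum calcium.

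| Section | Mother | Infant |
|---|---|---|
| 15, item 3a (screening) | urine, monthly | urine, monthly |
| 1.0 (stop rule) | urine and serum calcium | serum calcium |
| 4.0 (safety endpoints) | urine and serum calcium | serum calcium |
| 10.0 (procedures) | urine and blood | blood |
| 14.0 (exit) | hypercalciuria or hypercalcemia | hypercalcemia |
| 11.0 (specimens) | urine, source not stated | urine, source not stated |
| 12.0 (labelling) | blood and urine | blood and urine |

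The infant procedures in 10.0 are visits, questionnaires, drops, growth and health assessment, PEAPOD and blood. Urine is not among them. Sections 11.0 and 12.0 allow for urine, and 12.0 names the infant's, but neither gives a visit, a method or an assay.

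Counts from the readable text:

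- scheduled maternal urine collections: up to 4
- scheduled infant urine collections: 0
- printed upper-side urinary limits: 2 (0.8 and 1.0 mmol/mmol)
- printed upper-side serum calcium limits: 0
- printed lower-side serum calcium values: 1 (section 15, item 4)

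The infant therefore has no urine sample for the two printed limits, and the toxic limits that item 3a calls predefined have no serum calcium counterpart in the protocol.

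**Control group.** Item 3a extends monitoring to nonlactating mothers and formula-fed controls. Section 5.0 admits lactating women only, so item 3a departs from this design on a second point.

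**Units in section 15, item 4.** The one input from outside the documents is the molar mass of calcium, taken as 40.08 g/mol.

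1. The printed figure can be reproduced. The same item pairs 20 ng/mL of 25(OH)D with 50 nmol/L, a factor of 50 / 20 = 2.5. Applied to calcium, 7.5 × 2.5 = 18.75.
2. Direct conversion: 7.5 mg/dL = 75 mg/L, and 75 / 40.08 = 1.871 mmol/L, or about 1,871,000 nmol/L.
3. Ratio to the printed value: 1,871,257 / 18.75 ≈ 99,800, or about 100,000-fold.
4. Reading the printed unit as mmol/L does not repair it: 18.75 × 40.08 = 751.5 mg/L = 75.15 mg/dL, and 18.75 / 1.871 ≈ 10. A tenfold gap remains.

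**The case against.** The strongest reply is that the operative sections agree. Sections 1.0, 4.0, 10.0 and 14.0 all assign urine to mothers and serum calcium to infants. Only one paragraph of the risk section differs, and its control-group wording shows that it was not adapted to this design. Staff working from section 10.0 would know what to collect. This stands, and it limits the practical consequence. It does not remove the contradiction: item 3a is where the numerical limits are defined, and it states the safeguard for the infant in plain terms.

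A reader might infer that infants have no calcium monitoring. The documents do not support that. Infant serum calcium is a safety endpoint at the initial visit and at months 1, 2 and 3. Section 13.0 B sends out-of-range values to the DSMB. Section 15, item 4 rates the infant's risk of hypervitaminosis D as extremely low, and item 3 describes the sequence from urine to serum calcium for the woman.

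A reader might also infer that the serum calcium part of the stop rule has nothing behind it. That too goes further than the text. Section 1.0 refers to normal values, section 13.0 B gives the investigator a set of normative laboratory values, and section 14.0 attaches exit to infant hypercalcemia. Reference ranges are often held outside a protocol. What remains is narrow: item 3a speaks of predefined toxic limits for any outcome, yet the protocol prints only urinary ones and cites no source for the others.

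On the units, it is fair to say that the mg/dL value is usable alone and that the bracketed value looks like a conversion slip. It is still a wrong figure in a threshold for action.

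**Conclusion.** The inconsistency holds. Item 3a promises infant urinary screening and defines its limits on urine alone; the stop rule, endpoints, procedures and exit criterion provide urine or hypercalciuria checks for mothers only. As scheduled, the printed limits cannot be applied to infants. The reference to nonlactating and formula-fed controls does not belong to the enrolled population.

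The size is moderate: one stated infant safeguard that cannot operate as written, against serum calcium monitoring that does operate at four visits. No primary outcome is affected. The count of 0 infant urine collections rests on the readable text. Two figures are not shown, but the explicit infant list in section 10.0 makes a hidden schedule unlikely, and the other sections would still need reconciling if there were one.

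The unit pair in section 15, item 4 is wrong as printed, given 40.08 g/mol for calcium. It is a separate and smaller defect.

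This should be fixed. Which monitoring basis or threshold is right is not judged here.

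**What to change.** - Reconcile section 15, item 3a with sections 1.0, 4.0, 10.0, 11.0, 12.0 and 14.0, so that every limit applied to infants refers to an analyte that is actually collected from them.
- For each such limit, print the sponsor's own value or cite the document that holds it. This includes whatever item 3a means by predefined toxic limits other than the urinary ones.
- Remove the reference to nonlactating mothers and formula-fed controls.
- Reconcile the two calcium units in section 15, item 4.

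The cost is a wording amendment if item 3a is aligned with the existing schedule. If the sponsor keeps infant urine screening, a collection procedure has to be added. That choice is the sponsor's, and no threshold or clinical rule is proposed.
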